11.2.2 Pharmacokinetic Variables

Pharmacokinetic analysis of the plasma concentration data for total and released AZD4320 (and its metabolites (if available and appropriate)) when administered alone and in combination with voriconazole, when applicable, will be derived using non-compartmental methods in Phoenix® WinNonlin® Version 8.1 or higher (Certara); analysis will be performed by Covance on behalf of the sponsor.

PK analysis will, where data allow, be carried out using actual elapsed times determined from the PK sampling and dosing times in the database and following the schedule for plasma samples in [Table 7](#).

Table 7 Blood samples for plasma PK – Module 2

Study period	Day	Timepoint
Cycle 1 Period 1	Day 1	Pre-infusion
		30 minutes after the infusion the start of infusion (\pm 5 minutes)
		End of the infusion (+10 minutes)
		2 hours from start of Day 1 infusion (\pm 15 min)
		6 hours from start of Day 1 infusion (\pm 30 min)
		9 hours from start of Day 1 infusion (\pm 1 hour)
	Day 2	24 hours after the start of the Day 1 infusion (\pm 2 hours)
	Day 3	48 hours after the start of the Day 1 infusion (\pm 3 hours)
	Day 4	72 hours after the start of the Day 1 infusion (up to 3 hours before infusion on Day 4)
		End of the infusion on Day 4 (+10 minutes)
Cycle 1 Period 3	Day 15	Pre-infusion
		30 minutes after the infusion the start of infusion (\pm 5 minutes)
		End of the infusion (+10 minutes)

Study period	Day	Timepoint
		2 hours from start of Day 15 infusion (\pm 15 min)
		6 hours from start of Day 15 infusion (\pm 30 min)
		9 hours from start of Day 15 infusion (\pm 1 hour)
	Day 16	24 hours after the start of the Day 15 infusion (\pm 2 hours)
	Day 17	48 hours after the start of the Day 15 infusion (\pm 3 hours)
	Day 18	72 hours after the start of the Day 15 infusion (\pm 3 hours)
	Day 19	96 hours after the start of the Day 15 infusion (\pm 3 hours)
	Cycle 2	Pre-infusion
		End of the infusion (+10 minutes)
Cycle 3 and beyond	Day 1	Pre-infusion
		End of the infusion (+10 minutes)

If actual elapsed times are missing, nominal times may be used, with approval by the Sponsor; if this occurs, it will be described in the report. Nominal sampling times may be used for any agreed interim PK parameter calculations. Where data allow, the following PK parameters for total and released AZD4320 will be derived from plasma concentrations collected following doses administered on Cycle 1 Day 1 and Day 15.

Plasma

C_{\max}	Maximum observed plasma (peak) drug concentration
t_{\max}	Time to reach peak or maximum observed concentration or response following drug administration
λ_z	Terminal rate constant, estimated by log-linear least squares regression of the terminal part of the concentration-time curve
$t_{1/2\lambda_z}$	Half-life associated with terminal slope (λ_z) of a semi-logarithmic concentration-time curve
AUC_{0-72}	Partial area under the plasma concentration-time curve from time 0 to 72 hours after the start of infusion
AUC_{last}	Area under the plasma concentration-curve from time 0 to the last quantifiable concentration
t_{last}	Time of last observed (quantifiable) concentration
C_{trough}	Concentration prior to dosing

The following diagnostic parameters for plasma PK analysis will be provided:

λ_z lower	Lower (earlier) t used for λ_z determination
λ_z upper	Upper (later) t used for λ_z determination
$\lambda_z N$	Number of data points used for λ_z determination

λ_z lower	Lower (earlier) t used for λ_z determination
Rsq	Statistical measure of fit for the regression used for λ_z determination
Rsq adj	Statistical measure of fit for the regression used for λ_z determination adjusted for the number of used data points (n obs)
λ_z span ratio	Time period over which λ_z was determined as ratio of $t_{1/2}/\lambda_z$

The time period used for the estimation of apparent terminal elimination half-lives, where possible, should be over at least two half-lives. For $t_{1/2}$ estimates where λ_z was calculated over a time period less than twice their resultant half-life, the reliability of $t_{1/2}$ and any PK parameters derived from λ_z will be discussed in CSR.

Additional PK parameters may be calculated as appropriate.

11.2.3 Safety and Tolerability Variables

The primary objective is to assess the safety and tolerability of the AZD0466 in patients with advanced haematological malignancies.

As referenced in Section 3.2.3 the safety assessments performed will be:

- AE assessments,
- Clinical chemistry (including creatine phosphokinase) and haematology as described in Section 4.14.6,
- Amylase and lipase, coagulation indices, serum immunoglobulins, urinalysis, cardiac troponin and BNP (or NTproBNP), cortisol, ACTH and TSH parameters described in Section 4.14.6,
- Vital signs (SBP, DBP, pulse rate, oral body temperature), height and weight,
- 12-lead ECG,
- TLS (clinical and laboratory assessments),
- ECOG PS,
- Left ventricular ejection fraction (ECHO/MUGA).

The full list of laboratory measurements performed during the study that are used to evaluate safety and tolerability variables can be found in [Table 1](#) and [Table 2](#).

12 STATISTICAL METHODS - Module 2

12.1 Data Quality Assurance

Refer to Section 4.1.

12.2 General Presentation Considerations

Refer to the Section 4.2 for details of summary analyses. A clinical report will be produced from the database when all patients have had the opportunity to be treated and followed-up for 6 months.

12.3 General Variables

12.3.1 Data cut-off

Refer to Section 4.3.1 for general considerations. For this module a clinical report will be produced when all patients have had the opportunity to be treated and followed-up for 6 months.

12.3.2 Study Day Definitions

Refer to Section [4.3.2](#).

12.3.3 Time Windows

Refer to Section [4.3.3](#).

12.3.4 Handling of Missing Data

Refer to Section [4.3.4](#).

12.3.5 Imputation Rules for Laboratory Values Outside of Quantification Range

Refer to Section [4.3.5](#).

12.4 Software

Refer to Section [4.4](#).

12.5 Analysis Sets

Details of the analysis sets are presented in Table 8.

Table 8 Analysis Sets – Module 2

Population/Analysis set	Description
Safety	All patients who received at least one dose of AZD0466
Intention-to-treat	All patients who received at least one dose of AZD0466
Pharmacokinetics	Dosed patients with reportable plasma concentrations and no important AEs or protocol deviations that may affect PK

A summary on which analysis set will be used for each outcome variable is provided in Table 9.

Table 9 Summary of outcome variables and analysis sets – Module 2

Outcome variable	Analysis Set
Study Population/Demography Data	
Disposition	Enrolled
Demography and baseline characteristics	Safety
Important protocol deviations	Safety
Medical History	Safety
Prior/Concomitant Medication	Safety
Safety data	
Exposure	Safety
Adverse Events	Safety
Laboratory measurements	Safety
Vital Signs/ECG/Physical examination	Safety
ECOG PS	Safety
Efficacy Data	
Efficacy data listings	Intention-to-treat
Pharmacokinetics	
Pharmacokinetic variables	PK

PK pharmacokinetic.

The number of enrolled patients included/excluded from each of the analysis sets will be summarised. Patients and data excluded from each analysis set will be listed with the reason for exclusion.

12.6 Study Patients

12.6.1 Disposition of Patients

Refer to Section 4.6.1.

12.6.2 Protocol Deviations

Refer to Section 4.6.2.

12.7 Demographics and Baseline Characteristics

Refer to Section 4.7.

12.8 Medical/Surgical History

Refer to Section 4.8.

12.9 Concomitant Medications and Other Treatments

Refer to Section 4.10.

12.10 Efficacy Evaluation

All of the collected response related data, such as from complete blood count (CBC), extramedullary disease status, bone marrow core biopsy and aspirate will be listed for all patients in the Intention-to-treat analysis set. Summaries will not be produced.

12.11 Pharmacokinetics

For the definitions of handling, calculation and presentation of pharmacokinetic concentrations and parameters refer to Section 4.13.

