12.7.2 Sample Size Determination

The number of subjects is based on the desire to gain adequate information on the effect of voriconazole on the exposure of AZD4320, while exposing as few subjects as possible to study procedures.

Interpretation of the results will be based on the estimated effect (geometric mean ratio; GMR) and associated 90% CI.

Assuming an intrapatient CV of 30%, 10 PK evaluable participants are expected to give a relative precision of 2.0 (ratio between the upper and lower limits of the 90% CI) with a probability greater than 80%. This corresponds to a 90% CI of 2.83 to 5.66 if the observed ratio is 4.00 (based on in-vitro data). Up to 14 patients will be enrolled to ensure that at least 10 evaluable patients complete the study.

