Plasma concentrations of AZD4320 will be summarised by nominal sample time. Plasma concentrations and derived PK parameters will be summarised by dose level and cohort. Plasma concentrations at each timepoint will be summarised according to dose and cohort by

the following summary statistics:

- The geometric mean (g_{mean} , calculated as $\exp[\mu]$, where μ is the mean of the data on a logarithmic scale)
- Coefficient of variation (CV, calculated as $100 \sqrt{[\exp(s^2)-1]}$, where s is the standard deviation of the data on a log scale)
- $G_{\text{mean}} \pm$ standard deviation (calculated as $\exp[\mu \pm s]$)
- Arithmetic mean calculated using untransformed data
- Standard Deviation calculated using untransformed data
- Minimum
- Maximum
- Number of observations

The following summary statistics will be presented for the estimated PK parameters, as appropriate:

- G_{mean} , calculated as $\exp[\mu]$, where μ is the mean of the data on a logarithmic scale)
- CV, calculated as $100 \sqrt{[\exp(s^2)-1]}$, where s is the standard deviation of the data on a log scale)
- Arithmetic mean calculated using untransformed data
- Standard deviation calculated using untransformed data
- Minimum
- Maximum
- Number of observations

The pharmacokinetic data for AZD4320 will also be displayed graphically. Displays will include AZD4320 (total and released) plasma concentration subject profiles (on the linear and log scale) versus time and G_{mean} concentration (\pm standard deviation) versus time, stratified by dose.

Statistical Analysis of Pharmacokinetic Data

For the statistical analyses, only patients who provide eligible PK data for both AZD0466 (Period 1) and AZD0466 + Voriconazole (Period 3) interventions will be included for statistical comparison. A comparison of the AZD0466 PK parameters C_{max} and AUC will be performed for AZD0466 + Voriconazole versus AZD0466 interventions.

Where data allow, the statistical analysis will be performed via a linear mixed effect model using the natural logarithm of AZD4320 C_{max} and AUC as the response variables with

intervention as a fixed effect, and patient as a random effect. Transformed back from the logarithmic scale, geometric means together with CIs (2-sided 95%) for C_{max} and AUC will be estimated and presented. Also, ratios of geometric means together with CIs (2-sided 90%) will be estimated and presented.

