- Gmean (\pm gSD), Plasma Concentration Time Data (gSD calculated as $\exp[\mu \pm s]$)
- Gmean, Plasma Concentration Time Data - Semi-Logarithmic Scale

Individual figures will be plotted using concentration versus actual time, and mean figures will be plotted using concentration versus nominal time, by treatment or dose level and cycle/PK day, as needed.

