4.13.2 Pharmacokinetic Parameters Calculation and Summary

Derived PK parameters will be summarized by cycle, separately per cohort and actual dose level. The following summary statistics will be presented for the estimated PK parameters, as appropriate:

- Gmean (calculated as $\exp[\mu]$, where μ is the mean of the data on a logarithmic scale)
- gCV (calculated as $100 \sqrt{[\exp(s^2)-1]}$, where s is the standard deviation of the data on a logarithmic scale)
- Arithmetic mean calculated using untransformed data
- Arithmetic SD calculated using untransformed data
- Minimum
- Median
- Maximum
- Number of observations

The descriptive statistics for diagnostic parameters are n, arithmetic mean, SD, median, min, and max.

The following rules will be followed with regards to the number of decimal places and presentation of data in the tables and listings for PK parameters:

- Individual PK parameters will be presented to four significant digits, with the exception of t_{max} , which will be presented to two decimal places.

- Parameters derived directly from source data (e.g. C_{max}) shall be reported with the same precision as the source data (if this is not four significant digits).
- The mean, geometric mean, median and SD values will be reported to four significant digits, all other descriptive statistics will be reported to three significant digits except for CV% which will be presented to one decimal place.
- For t_{max} the minimum and maximum will be presented to two decimal places and all other descriptive statistics will be presented to three decimal places.
- Estimates and confidence intervals in the form of percentages will be presented to two decimal places.

4.13.3 Criteria for Handling Concentrations Below the Limit of Quantification or Missing Concentrations in Pharmacokinetic Analysis

For the non-compartmental analysis (NCA) and individual plot, if a BLQ value occurs before the first measurable concentration, it will be treated as zero. Thereafter, BLQ values will be treated as missing for PK analysis, with special situations described below. The following rules apply with special situations defined below:

- Where 2 or more consecutive concentrations are BLQ at the end of a profile, the profile will be deemed to have terminated and any further quantifiable concentrations will be set to missing for the calculation of the PK parameters unless they are considered to be a true characteristic of the profile of the drug.

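### Module 2: the SAP does not carry over the paired geometric mean ratio and 90% CI on which the protocol reads the voriconazole interaction, and it lists AUClast as an interaction endpoint over unequal sampling windows

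*SAP*

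**What the plan says.** **Protocol.** Section 12.7.2: "Interpretation of the results will be based on the estimated effect (geometric mean ratio; GMR) and associated 90% CI". It sizes the module on that interval (intrapatient CV 30%, 10 evaluable patients, upper/lower limit ratio 2.0 with probability above 80%) and adds: "Up to 14 patients will be enrolled to ensure that at least 10 evaluable patients complete the study". Section 12.7.8.1 restricts the comparison: "only patients who provide eligible PK data for both AZD0466 (Period 1) and AZD0466 + Voriconazole (Period 3) interventions will be included". Where data allow, log Cmax and log AUC of AZD4320 go into a linear mixed model with intervention fixed and patient random, and "ratios of geometric means together with CIs (2-sided 90%) will be estimated and presented". Section 12.7.4 leaves technical detail to the SAP.

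**SAP.** Section 10.1 keeps the interaction objective, with Cmax, AUC0-72 and AUClast for total and released AZD4320, alone and with voriconazole. Section 11.2.2 derives these after the Day 1 and Day 15 doses. Section 12.11, on analysis, is one sentence: "For the definitions of handling, calculation and presentation of pharmacokinetic concentrations and parameters refer to Section 4.13". Section 4.13.2 then says: "Derived PK parameters will be summarized by cycle, separately per cohort and actual dose level". The one trace of an inferential output there is a rounding rule: "Estimates and confidence intervals in the form of percentages will be presented to two decimal places". Section 4.2 sets general CI levels of 80% and 95%. Section 12.13 calls the sample size empirical. Section 13 declares only the Module 1 efficacy change.

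**The concern.** The SAP retains the objective and derives the inputs, but does not specify the quantity by which the protocol reads the result. A programmer following the SAP would produce summaries of Day 1 and Day 15 exposure without a paired ratio, without the restriction to patients with both profiles, and without a 90% CI. A reader cannot tell whether the analysis was dropped on purpose or overlooked. SAP 8.11 states that Module 1 PK will have no formal statistics; nothing similar is said for Module 2.

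The second issue is AUClast. In SAP Table 7 the Day 1 profile ends at about 72 h, because the Day 4 infusion follows, while the Day 15 profile runs to 96 h. If the last Day 15 sample is quantifiable, a Day 15/Day 1 AUClast ratio covers a longer period in the numerator and exceeds 1 with no interaction.

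**Working it through.** **1. The protocol's precision statement reproduces.** Inputs from protocol 12.7.2: CV 30%, n = 10, 90% CI. Within-patient log SD: s = √ln(1 + 0.30²) = 0.2936. Paired half-width on the log scale: t(0.95, 9) × s × √(2/10) = 1.833 × 0.1313 = 0.2407, a factor of 1.272. Around an observed 4.00 the expected interval is 3.14 to 5.09, so upper/lower = 1.62. The chance that upper/lower is at most 2.0 is P(χ²₉ ≤ 9·smax²/s²) with smax = ln 2/(2t√(2/10)), which gives 97%, above the stated 80%. The illustrated 2.83 to 5.66 is 4.00/√2 to 4.00 × √2. At the SAP's general levels the expected interval would instead be 3.34 to 4.80 (80%) or 2.97 to 5.38 (95%).

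**2. Fewer pairs.** The number of patients with both profiles after termination is not stated. By the same formula, expected upper/lower is 4.05, 2.66 and 2.21 at 3, 4 and 5 pairs, against the protocol's target of 2.0. It reaches 1.98 at 6 pairs.

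**3. AUClast window.** No half-life or quantification limit is given, so half-lives of 12 to 72 h are assumed. With k = ln 2/half-life, no interaction and a quantifiable 96 h sample, ratio = (1 − e^(−96k))/(1 − e^(−72k)). The ceiling for a flat curve is 96/72 = 1.33. A release-limited curve (the same values as release half-lives, with assumed elimination half-lives of 2 to 4 h) gives 1.01 to 1.23, so the mono-exponential form is not critical here.

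**4. Residual drug on Day 15.** Doses are from protocol Table 22. Relative to Day 1, Day 4 is 1.5 to 2 times (3600/2400; 150/75) and Day 8 is 2.25 to 4 times (5400/2400; 300/75). Time to the Day 15 dose is 336, 264 and 168 h from Days 1, 4 and 8. Treating each infusion as a bolus with mono-exponential decline, the pre-dose residual in units of one Day 1 dose is R = e^(−336k) + d4·e^(−264k) + d8·e^(−168k). The no-interaction AUC0-72 ratio is then 1 + R.

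| Assumed half-life | Window effect on AUClast | R | AUC0-72 ratio from residual alone |
|---|---|---|---|
| 12 h | 1.01 | < 0.001 | 1.00 |
| 24 h | 1.07 | 0.018–0.032 | 1.02–1.03 |
| 48 h | 1.16 | 0.24–0.41 | 1.24–1.41 |
| 72 h | 1.21 | 0.60–0.99 | 1.60–1.99 |

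Worked case, 48 h, 75/150/300 mg: 0.0078 + 2 × 0.0221 + 4 × 0.0884 = 0.41.

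In this model Cmax is inflated by the same 1 + R. The pre-dose level as a share of the Day 15 peak is R/(1 + R): about 2–3% at 24 h, 19–29% at 48 h and 38–50% at 72 h. The already scheduled pre-dose sample would therefore show which case applies.

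**The case against.** The protocol model applies only where data allow. Recruitment stopped early, and SAP version 2.0 aligned its analysis descriptions with the outputs planned for a synoptic report. The SAP cites protocol version 4.0, whose specification its silence does not repeal, and output specifications sit in a separate document. All of this stands: the documents do not show whether the omission was deliberate, or that the analysis will be missing from the final outputs. It does not explain why Section 13 is silent, or why Section 12.13 keeps a rationale that, per protocol Appendix R, was replaced in Amendment 2.

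A reader might infer that the SAP makes Day 1 and Day 15 indistinguishable, because 4.13.2 groups by cycle, cohort and dose and both profiles fall in Cycle 1 at equal doses. That goes too far. Section 4.13.1 summarises concentrations and parameters at each time point, Section 11.2.2 derives parameters for both days, and the figure rule plots "by treatment or dose level and cycle/PK day, as needed". The two days can be summarised separately; what is missing is the paired ratio and its interval.

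A reader might also say that the SAP compares AUClast over unequal windows. Section 10.1 lists endpoints and defines no ratio; the distortion arises only if a ratio is formed. AUC0-72, on the same line, has matched windows.

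Finally, protocol 12.1.3 wants the result to inform azole restrictions in ongoing and future modules. With the study terminated, no module of this study remains to be informed, so the consequence is for the reporting of this objective.

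**Conclusion.** The point holds as a gap between protocol and SAP that should be closed. The SAP as written does not specify the analysis on which the protocol bases interpretation, and does not declare its removal. This rests on the text alone.

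The sizes are conditional. The AUClast window effect is about 1% to 21% for assumed half-lives of 12 to 72 h, and requires a quantifiable 96 h sample. Against the ratio of 4.00 that the protocol uses as its illustration, the lower end is immaterial.

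Two stronger conclusions are not supported. First, AUC0-72 does not remove all bias: it fixes the window, but with a half-life of 48 h or more residual drug would distort the ratio by more than the window does. Up to 24 h the residual is negligible to about 3%. These figures assume bolus dosing and mono-exponential decline. Second, it cannot be said that a handful of pairs would still satisfy the protocol: 3 to 5 pairs give an expected upper/lower of 4.05 to 2.21, short of the 2.0 target.

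**What to change.** (a) State the protocol's analysis in SAP 12.11, where data allow: log Cmax and log AUC0-72 for total and released AZD4320; intervention fixed, patient random; only patients with both Period 1 and Period 3 data; Day 15/Day 1 geometric mean ratio with 2-sided 90% CI. If too few pairs remain, list individual Day 15/Day 1 ratios and record the change with its reason in Section 13. Align Section 12.13 with protocol 12.7.2.

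(b) Use AUC0-72, or AUClast capped at 72 h on both days, for the ratio. Keep uncapped AUClast descriptive.

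(c) Report the Day 15 pre-dose concentration relative to Day 15 Cmax beside the ratio. If it is not negligible, add a sensitivity ratio with the Day 15 profile corrected for the pre-dose residual, using the estimated terminal slope.

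**Cost.** A few lines of SAP text and four small models (two parameters, two analytes) on samples already scheduled. A 72 h window may understate an interaction if the half-life is long, the interval will be wide with few pairs, and the residual correction depends on the estimated slope. The last Day 1 sample may be drawn up to 3 h before the Day 4 infusion, so part of AUC0-72 may need extrapolation: (e^(−69k) − e^(−72k))/(1 − e^(−72k)) = 0.3% to 2.9% for the assumed half-lives.

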12.12 Safety and Tolerability Evaluation

Safety, tolerability data will be listed and summarized as defined by the current AZ standards (oncology early phase study outputs). Safety analysis set will be used for all safety and tolerability analyses. All listings and tables will be based on the safety analysis set

This include the AEs, AESIs, laboratory data, vital signs, and ECG as safety assessments.

Additional assessments will be included: ECHOs and serum immunoglobulins.

12.12.1 Exposure and treatment administration

For the calculation and presentation of exposure and treatment administration for AZD0466 refer to Section 4.14.1.

In addition, the exposure to voriconazole received will be listed for all patients. Actual and total treatment duration will be summarized by the following: mean, standard deviation, minimum, maximum, median and number of observations.

